Therefore, we propose to perform a prospective randomized pilot clinical trial, stratified by primary tumor site, to evaluate the degree of xerostomia and quality of life (QOL) in subjects with HN-SQCC treated with radiation therapy under margin-based and robust radiotherapy treatment plans. Margin-based plans will use both biological (biological optimization) and physical objectives whereas robust planning will use physical objectives for sparing of the parotid glands. Intensity-modulated radiation therapy (IMRT) and standard chemotherapy will be used. QOL (quality of life) will be measured using the EORTC QLQ-C30 questionnaire and EORTC QLQ-H&N35 (head and neck) module before radiotherapy (baseline) and then 3, 6, 9 and 12 months after radiotherapy. Xerostomia will be measured in study subjects using two patient-reported scoring systems completed by each subject before radiotherapy and then 3, 6, 9, and 12 months after radiotherapy: the LENT/SOMA grading system and the University of Michigan's Xerostomia Questionnaire (XQ; see Eisbruch *et al.* 2001). The data collected by this randomized pilot clinical trial will be used to inform the design of, and decision-making for, future larger studies that seek to compare different methods of radiotherapy planning in the treatment of HN-SQCC.

STUDY OBJECTIVES

Primary Objective

To evaluate descriptively over time the prevalence and grade of xerostomia in subjects treated for HN-SQCC with IMRT under either biologically optimized margin-based or robust photon radiotherapy.

Secondary Objectives

- 1) To compare descriptively the arm treated with IMRT under the margin-based radiotherapy plan to the arm treated with IMRT under the robust radiotherapy plan for possible differences in derived outcomes of interest, including but not limited to: (1) occurrence rate of grade ≥ 2 xerostomia as determined using the LENT/SOMA scale; and (2) occurrence rate of overall score ≥ 30 on the XQ.
- 2) To obtain NTCP values of the parotid glands from both margin-based and robust radiotherapy treatment plans using validated parameter values of the NTCP mean dose model. Each subject will have their parotid NTCP values computed under both plans, even though they will receive IMRT delivered under only the plan they are randomized to.
- 3) To obtain dose statistics for dose delivered to the parotid glands of each subject via either margin-based or robust treatment plans.

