- 4) To determine quality of life (QoL) at baseline and at 3, 6, 9 and 12 months following treatment using the EORTC QLQ-C30 instrument combined with the EORTC QLQ-H&N35 module. The main scores of interest at each time point will be the global QoL scale and the individual scales for dry mouth, oral pain, swallowing, opening mouth, sticky saliva, and social eating.
- 5) To correlate NTCP values with change in QoL results.

STUDY POPULATION

Research subjects will be recruited from the Radiation Oncology clinic on the UAMS campus. The potential research subject will be identified by the physician during their routine clinic visit. Prior to any research activities, the subject will be approached for participation in the study by their physician or staff member, who will discuss the protocol along with the risks and potential benefits of participating in it. Subjects currently taking saliva stimulating drugs will be asked if they are willing to discontinue such drugs in order to participate. A clear statement will be made concerning the voluntary nature of participation and that the decision will have no effect on their remaining care.

We plan to consent up to 75 subjects in order to reach our maximum accrual of 50 subjects, randomized to the two study arms. Eligibility waivers are not permitted. Subjects must meet all of the inclusion and exclusion criteria to be enrolled in the study. Study procedures may not begin until a subject is consented.

Inclusion criteria

1. Histological documentation of HN-SQCC
2. Older than 21 years of age
3. Subject is eligible for routine chemo-radiotherapy for treatment of HN-SQCC
4. Informed consent is obtained
5. Karnofsky performance status of at least 70 points

Exclusion criteria

1. Women with a positive urine pregnancy test are excluded from this study; women of childbearing potential (defined as those who have not undergone a hysterectomy or who have not been postmenopausal for at least 24 consecutive months) must agree to refrain from breast feeding and practice adequate contraception
2. Unable to comply with study procedures

3. Use of saliva stimulating prescription drugs such as Evoxac or Salagen

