This study also has the following secondary objectives:

- 1) To compare descriptively the arm treated with IMRT under the margin-based radiotherapy plan to the arm treated with IMRT under the robust radiotherapy plan for possible differences in derived outcomes of interest, including but not limited to: (1) occurrence rate of grade ≥ 2 xerostomia as determined using the LENT/SOMA scale; and (2) occurrence rate of overall score ≥ 30 on the XQ.
- 2) To obtain NTCP values of the parotid glands from both margin-based and robust radiotherapy treatment plans using validated parameter values of the NTCP mean dose model. Each subject will have their parotid NTCP values computed under both plans, even though they will receive IMRT delivered under only the plan they are randomized to.
- 3) To obtain dose statistics for dose delivered to the parotid glands from both margin-based and robust treatment plans.
- 4) To determine quality of life (QoL) at baseline and at 3, 6, 9 and 12 months after treatment using the EORTC QLQ-C30 instrument combined with the EORTC QLQ-H&N35 module. The main scores of interest at each time point will be the global QoL scale and the individual scales for dry mouth, oral pain, swallowing, opening mouth, sticky saliva, and social eating.
- 5) To correlate NTCP values with change in QoL results.

To accomplish this study's secondary objectives, the analysis will proceed as follows:

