- 1) Xerostomia grades from the LENT/SOMA scale will be dichotomized as grade ≥ 2 versus grade < 2 , then summarized by treatment arm and time point as the number and proportion achieving grade ≥ 2 . The dichotomization is placed at grade $</\geq 2$ because that was the cutpoint used in the PARSPORT study [22], but we will also consider an alternative dichotomization at grade $</\geq 3$. As for the overall XQ score (a continuous variable), we will dichotomize it at different cutpoints chosen for their potential clinical relevance, beginning with a cutpoint of $</\geq 30$, then summarize the result by treatment arm and time point as the number and proportion of subjects who surpass the cutpoint. For all dichotomized versions of both xerostomia measures, the proportions on each arm and proportion differences between treatment arms will be estimated at each time point. Estimated proportions and their differences will be accompanied by two-sided 90% confidence intervals. Exploratory mixed-models analysis may be used in follow-up mode, as time permits, to explore more deeply the differences between treatment arms and how they change over time.
- 2) NTCP values from both plans will be summarized by plan and treatment arm as the mean, SD, median, quartiles, and range. Data will be graphed using box plots versus treatment arm. Plans will be compared descriptively by calculating the paired difference between them, and summarizing the result as means, SDs, and ranges. Means will be accompanied by 90% confidence limits.
- 3) Dose statistics on each subject (i.e., the mean, SD, median, 1st and 3rd quartiles, 5th percentile, and 95th percentile of dose received by the subject) will be summarized by statistic and treatment arm as the mean, SD, median, quartiles, and range. Data for each statistics will be graphed using box plots versus treatment arm.
- 4) The global EORTC QOL scale and individual scales for dry mouth, oral pain, swallowing, opening mouth, sticky saliva, and social eating will be summarized by treatment arm and time point as the mean, SD, and range, and also (for individual Likert-scaled items that have 5 or fewer ordered categories) as the

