number and proportion of subjects whose answer falls into each ordered category. Data will be graphed using box plots or scatter plots versus treatment arm and profile plots versus time point. In general, the mean differences between treatment arms will be estimated at each time point, and such estimates will be accompanied by two-sided 90% confidence intervals. Exploratory mixed-models analysis may be used in follow-up mode, as time permits, to explore more deeply the differences between treatment arms and how they change over time.

- 5) Changes in QoL results after treatment (compared to baseline) will be calculated at each post-treatment time point, then assessed for correlation with NTCP values by Spearman correlation analysis.

For analyses in support of the secondary objectives, the outcomes at all time points will be of interest, but outcomes at the 12-month time point will be of special interest because of this time point's prominence in previous studies such as PARSPORT [22].

Sample-size considerations. We plan to consent up to 75 subjects in order to reach our maximum accrual of 50 subjects. Twenty-five subjects will be assigned randomly to IMRT under the margin-based radiotherapy plan, and 25 subjects will be assigned randomly to IMRT under the robust radiotherapy plan.

The IMRT arm of the PARSPORT study [22] lost 17% of its enrolled subjects to death and dropout before they could be evaluated at 12 months for that study's primary endpoint, grade ≥ 2 xerostomia. If similar results hold in our study, and if we enroll 25 subjects per treatment arm, then we can expect the number of subjects who remain on each treatment arm for 12 months to be binomially distributed with expected value of 20.75 and 95% probability of being 18 or higher.

In each analysis, the precision of the estimates can be quantified through their standard errors, with smaller standard errors denoting greater precision. At 3 months, when each treatment arm should still contain 25 subjects, the standard

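### Does the parotid NTCP analysis need a stated gland, unit and plan before secondary objectives 2 and 5 can be trusted?

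*Combined protocol and SAP*

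**What the plan says.** Secondary objective 2, in Study Objectives and again in Statistical Considerations, is "To obtain NTCP values of the parotid glands from both margin-based and robust radiotherapy treatment plans", using a mean dose model. It adds that "Each subject will have their parotid NTCP values computed under both plans", although only the randomized plan is delivered.

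The analysis text for objective 2 states that "NTCP values from both plans will be summarized by plan and treatment arm". It continues "Plans will be compared descriptively by calculating the paired difference between them", and then "Means will be accompanied by 90% confidence limits".

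Objective 5 is "To correlate NTCP values with change in QoL results". Its analysis text calculates the change in QoL from baseline at each post-treatment time point, "then assessed for correlation with NTCP values by Spearman correlation analysis". The QoL scores are those of objective 4: "The main scores of interest at each time point will be the global QoL scale and the individual scales for" six named symptoms or functions, so seven scores at 3, 6, 9 and 12 months.

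The Measures section has entries for xerostomia, quality of life, and demographic and clinical characteristics, and none for NTCP. Study Procedures says that one of the two strategies is used to plan treatment. It does not describe how the second, undelivered plan is prepared.

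**The concern.** A subject has two parotid glands and two plans, so up to four NTCP values. The text fixes the plan dimension for objective 2 (both plans, paired) but not the gland dimension. Two analysts could both follow it, one reporting 50 differences and the other 100, with different standard deviations and interval widths. Two glands in one head share the same anatomy, tumour and pair of plans, so their differences are probably correlated. Ignoring that would make the 90% limits too narrow. The sample-size text says the pilot's estimates should be precise enough to inform larger studies, so an overstated precision would matter.

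For objective 5, neither gland nor plan is named, which leaves room to choose after the correlations are seen. In an open-label trial, a research-only plan might also receive less care than the plan to be delivered. The paired difference would then mix planning strategy with planning effort.

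**Working it through.** **The plan's own precision figures.** Inputs from the sample-size considerations: 25 subjects per arm and 17% loss by 12 months.
- Expected number remaining: 25 × 0.83 = 20.75. P(X ≥ 18) for a binomial(25, 0.83) is 0.9505. Both match the stated values.
- SE of a mean in SD units: 1/√25 = 0.200 and 1/√18 = 0.236. Both match.

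These figures are offered for each analysis, and n is the number of subjects.

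**Which unit the text implies.** Objective 2 assigns NTCP values to each subject. The next analysis item, on dose, starts from statistics computed on each subject and then summarizes them by arm. The precision figures count subjects. No sentence counts glands.

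**What a gland-level analysis would cost.** Let s be the SD of the gland-level plan difference, taken as equal on both sides, and ρ the correlation between a subject's two glands. The documents give neither, so ρ is shown over a range.
- 100 glands treated as independent: t(0.95, 99)/√100 = 1.660/10 = 0.166 s.
- Mean of two glands, 50 subjects: t(0.95, 49)/√50 × √((1+ρ)/2) = 0.237 × √((1+ρ)/2) s.
- One named gland per subject, 50 subjects: 0.237 s.

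| ρ | Half-width, mean of two glands | 0.166 s divided by that | Simulated coverage of the 100-gland interval |
|---|---|---|---|
| 0 | 0.168 s | 0.99 | 90.1% |
| 0.3 | 0.191 s | 0.87 | 85.1% |
| 0.5 | 0.205 s | 0.81 | 82.0% |
| 0.8 | 0.225 s | 0.74 | 77.8% |

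The shortfall of 13%, 19% and 26% therefore belongs only to the 100-independent-glands analysis.

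**What remains open on the subject-level reading.** The choice is between one gland and a two-gland summary. The mean of two gives a half-width of 0.191 to 0.225 s for ρ from 0.3 to 0.8, against 0.237 s for one gland. That is 0.81 to 0.95 of the width. Each is a proper 90% interval for its own quantity, so neither is wrong.

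**Objective 5.** Seven scores × 4 time points = 28 correlations, or 56 if each gland is used separately. The 28 exist even when gland and plan are fully named, so the missing definition does not create them. The plan attaches no test or interval to these correlations. Only a delivered dose can affect later QoL, so the undelivered plan is not a credible partner for QoL change.

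**Undelivered plan.** Let D be the true mean difference (margin-based minus robust) and e the NTCP offset from less care on the undelivered plan. The undelivered plan is robust in the margin-based arm and margin-based in the robust arm. The arm means are then D − e and D + e. Pooled at 25 per arm: [25(D − e) + 25(D + e)]/50 = D. The planned summary by plan and arm gives four means, and subtracting the two within each arm recovers D − e and D + e. A sizeable offset would therefore show in output already planned, apart from chance differences between arms.

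**The case for a change.** The strongest case for a change is that the document defines its other derived outcomes carefully. The XQ is eight items summed to a 0–80 score, and LENT/SOMA and the XQ have stated cutpoints. NTCP has no such rule, and a few sentences would supply one. The subject-level reading, however natural, does not say how two glands become one value. An equal effort offset cancels only in the pooled mean, not within an arm, and an unequal one does not cancel at all.

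The facts in this stand. The gland or summary is not named, objective 5 does not name the plan, and the preparation of the second plan is not described.

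The inference to a faulty result does not stand. The narrowing and undercoverage need an analysis that the text does not state and that its subject-based precision figures argue against, together with an assumed positive correlation. Selection among objective 5 correlations is a limited hazard where nothing is tested and no decision depends on the result. The plan also already singles out 12 months as the time point of special interest for the secondary objectives. The effort offset is a possibility with no size. Study Procedures describes both strategies as standard at the institution, and Study Objectives follows an introduction that states the type of optimization objective each strategy uses. Who prepares a research plan, and when, is operational detail.

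**Conclusion.** No change to the plan follows. The text leaves out a definition, but it contains no contradiction and no stated figure is wrong. Read as its own wording suggests, with one value per subject, the difference taken within subject and the delivered plan used for objective 5, the 90% limits for objective 2 are sound and the objective 5 correlations are interpretable. The gland choice changes the interval width to between 0.81 and 0.95 of the one-gland width for ρ from 0.3 to 0.8, and it does not affect validity. The 13% to 26% shortfall would arise only if an analyst counted two glands per subject as independent, which a competent statistician would avoid.

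This conclusion assumes subject-level analysis, and ρ and a common s are assumptions that the documents do not supply. The opening part of the background was not available, so a definition given there cannot be ruled out. Both objectives are secondary and descriptive in a pilot without hypothesis tests, and the primary xerostomia analysis does not use NTCP.

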All other adverse events, such as those that are expected, or are unlikely or definitely not related to the study participation, are to be reported annually as part of regular IRB continuing review.

STATISTICAL CONSIDERATIONS

This is a randomized, two-arm, open-label pilot clinical trial conducted in subjects with squamous-cell carcinoma of the head and neck. Its primary objective is to evaluate descriptively over time the prevalence and grade of xerostomia in subjects treated with IMRT under either biologically optimized margin-based or robust photon radiotherapy of HN-SQCC. Xerostomia will be measured in study subject using two patient-reported scoring systems completed by each subject before radiotherapy and 3, 6, 9, and 12 months after radiotherapy: the LENT/SOMA grading system and the University of Michigan's Xerostomia Questionnaire (XQ; see Eisbruch *et al.* 2001).

To accomplish this study's primary objective, the analysis will proceed as follows: To analyze the XQ, scores on its 8 items will be summed for each subject at each time point to produce an overall XQ score whose values theoretically can range from 0 to 80; it will be treated as a continuous variable. LENT/SOMA grades as written on the form will simply be recorded electronically, and non-integer grades will be allowed if that's what the subject wrote on the form. Longitudinal LENT/SOMA grades will be summarized by treatment arm and time point as the number and proportion of subjects achieving each grade, and also as the mean and SD of grade. Longitudinal overall XQ scores will be summarized by treatment arm and time point as the mean, SD, median, quartiles, and range. Both the correlation between xerostomia measures within each time point and the correlation within each xerostomia measure across time points will be studied using Spearman correlation analysis. Estimated means, SDs, medians, and quartiles will be accompanied by 90% confidence intervals. In exploratory analysis,

we will employ mixed-models analysis to investigate more deeply the interrelationships among the xerostomia measures between treatment arms and time points. Also in exploratory analysis to accomplish the primary objective, we will use means, SD, and ranges to summarize each of the 8 individual items from the XQ by treatment arm and timepoint, and investigate using mixed-models approaches to compare the XQ items descriptively for treatment-arm differences over time.

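### The planned arm differences on the seven EORTC scales name no baseline covariate; prespecified ANCOVA on the pre-radiotherapy score may narrow the 90% intervals if baseline and follow-up correlate above about 0.18 (18 per arm)

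*Combined protocol and SAP*

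**What the plan says.** The trial background, just before the study objectives, has the EORTC questionnaires completed "module before radiotherapy (baseline) and then 3, 6, 9 and 12 months after radiotherapy". A baseline score is therefore planned for all seven scales of interest: global QoL, dry mouth, oral pain, swallowing, opening mouth, sticky saliva and social eating.

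Under Statistical Considerations, the analysis for secondary objective 4 summarises these scales by arm and visit. It then states: "In general, the mean differences between treatment arms will be estimated at each time point", each with a two-sided 90% interval. No method and no covariate is given. The only model mentioned for these scales is optional: "Exploratory mixed-models analysis may be used in follow-up mode, as time permits". Its terms are not listed.

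The one analysis step that pairs baseline with follow-up is for secondary objective 5: "Changes in QoL results after treatment (compared to baseline) will be calculated at each post-treatment time point". Those changes are then correlated with NTCP; they are not used to compare the arms.

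Two neighbouring analyses mark the limits of the point:

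- **XQ total.** The primary analysis says: "Longitudinal overall XQ scores will be summarized by treatment arm and time point as the mean, SD, median, quartiles, and range". No arm difference is scheduled for the continuous score.
- **Correlations over time.** These are planned only for xerostomia: "the correlation within each xerostomia measure across time points will be studied using Spearman correlation analysis". Nothing equivalent is planned for the EORTC scales.

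**The concern.** With 18 to 25 subjects per arm, the interval for an arm difference is wide, and chance differences at baseline can be sizeable. At 18 per arm the standard error of a baseline arm difference is sqrt(2/18) = 0.333 SD, so about 32% of trials would show a larger imbalance than that on a given scale. A raw follow-up difference carries r times that imbalance. Adjusting for the baseline score removes this part and, if r is large enough, narrows the interval at no cost in data.

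The pilot exists to inform larger trials. Two things are at stake: the width of the intervals it passes on, and the EORTC baseline-to-follow-up correlations, which a later trial needs in order to judge what baseline adjustment is worth. The plan does not commit to reporting them. Leaving the estimator open also leaves the choice between raw, change-score and adjusted differences until after the data are seen.

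**Working it through.** **The plan's own figures reproduce.** From Sample-size considerations, with 17% loss by 12 months:

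- Expected number per arm: 25 × 0.83 = 20.75.
- P(X ≥ 18), X binomial(25, 0.83): 0.9505, stated as 95%.
- SE of an arm mean: 1/√25 = 0.200 SD and 1/√18 = 0.236 SD.

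These are single-arm figures. Baseline adjustment does not change them; it affects only the interval for the arm difference.

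**Inputs.** n = 18 per arm (the plan's low case at 12 months) and n = 25 (its 3-month case), with 90% two-sided intervals. The correlation r is not in the documents and is assumed to lie between 0 and 0.7.

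**Formulas**, in units of the follow-up SD, for a normal baseline score:

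- Raw: SE = sqrt(2/n); half-width = SE × t(0.95; 2n − 2).
- ANCOVA: SE = sqrt(2/n) × sqrt[(1 − r²)(1 + 1/(2n − 4))]; half-width = SE × t(0.95; 2n − 3).

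For n = 18: raw = 0.3333 × 1.6909 = 0.564. At r = 0.5: 0.3333 × sqrt(0.75 × 33/32) × 1.6924 = 0.2931 × 1.6924 = 0.496.

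| n per arm | Raw | r = 0 | r = 0.3 | r = 0.5 | r = 0.7 | Break-even r |
|---|---|---|---|---|---|---|
| 18 | 0.564 | 0.573 | 0.546 | 0.496 | 0.409 | 0.179 |
| 25 | 0.474 | 0.480 | 0.458 | 0.415 | 0.343 | 0.149 |

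The adjusted-to-raw ratios are 1.016, 0.970, 0.880 and 0.726 at n = 18, and 1.011, 0.965, 0.876 and 0.722 at n = 25. At 21 per arm, close to the expected 12-month count, break-even is about 0.16.

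Break-even refers to expected width. In simulation at r = 0.18, the adjusted interval was the narrower one in 41% of trials at 18 per arm and 47% at 25.

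**Coarse items.** The plan itself makes provision "for individual Likert-scaled items that have 5 or fewer ordered categories", so the normal-score figures are only approximate for such scales. A simulation covered this: 20,000 trials per setting, 18 per arm, no true difference, and a latent normal pair cut into four categories scored 0, 33.3, 66.7 and 100. All category frequencies were assumed: follow-up 15/30/30/25%; baseline 40/35/15/10%, 60/25/10/5% or 80/12/5/3%. Ranges are over the three baseline patterns.

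| Latent r | Observed r | Mean half-width, adjusted/raw | Adjusted interval narrower in |
|---|---|---|---|
| 0 | – | 1.016 | 20–21% of trials |
| 0.3 | 0.19–0.25 | 0.983–0.998 | 44–57% |
| 0.5 | 0.32–0.42 | 0.921–0.966 | 72–88% |
| 0.7 | 0.43–0.60 | 0.815–0.919 | 92–99% |

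Coverage of the adjusted 90% interval was 0.899 to 0.904, against 0.897 to 0.905 for the raw one. With 80% of subjects at the floor, baseline had no variation in 25 of 80,000 trials; with the other two patterns this never happened.

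**The case against.** The strongest reply is that nothing is broken. This is a descriptive pilot, no test or decision rule depends on these intervals, the raw difference is valid, and the plan already judges its precision sufficient. All of that stands, and it is why this is a recommended improvement and not a correction.

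The second reply is that the gain rests on an unknown r. Baseline precedes the radiation whose effects are being measured, and the documents do not support a high correlation. This also stands. On the simulated 0–100 item the raw half-width is about 19.0 points. Adjustment gives 18.7–18.9 at latent r = 0.3 and 17.5–18.4 at 0.5, so a 27% gain should not be expected on such items. But the trade is lopsided: the expected loss at r = 0 is 1.6%, while r = 0.5 on a normal score gives the raw interval of about 23 per arm with only 18.

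Three smaller points are fair:

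- By-visit summaries would let a reader see a baseline imbalance. Seeing it does not remove it from the follow-up difference.
- ANCOVA needs both scores. At r = 0.3, 17 pairs per arm give 0.564 SD, the same as the raw interval at 18, so losing one pair per arm cancels the gain. Baseline forms are completed on consent, so few losses are likely.
- Randomisation is stratified by primary tumor site, and the figures here include no site term.

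**Conclusion.** The point holds, as an inexpensive improvement in efficiency. The scheduled EORTC arm differences make no committed use of a baseline score that is already collected. Prespecified adjustment changes the expected 90% half-width at 18 per arm by between +1.6% (r = 0) and −27% (r = 0.7), with break-even at r = 0.18; at 25 per arm break-even is 0.15. For coarse items with 40–80% of subjects at the baseline floor, the mean narrowing is 0–2%, 3–8% or 8–19% at latent r of 0.3, 0.5 or 0.7.

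These sizes rest on the assumed range of r, normal scores in the closed-form figures, assumed category frequencies in the simulation, and no site term. The documents cannot settle where r lies, so the claim is that the intervals may narrow, not that they will.

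**What to change.** In the SAP text for secondary objective 4, prespecify one estimator:

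- For each of the seven scales at 3, 6, 9 and 12 months, fit an ANCOVA of the follow-up score (not the change score) on arm and that scale's baseline score, in subjects with both. Report the adjusted arm difference with its two-sided 90% interval as the main estimate.
- Keep the planned raw summaries and raw differences as supporting results. If a scale has no baseline variation, report the raw difference only.
- Report the baseline-to-follow-up correlation for each EORTC scale.
- Say whether primary tumor site enters the model. If it does, the figures above need recomputing.
- For the continuous XQ total, add the same adjusted difference, labelled as a new secondary descriptive analysis.
- Leave the dichotomised xerostomia analysis as written ("the proportions on each arm and proportion differences between treatment arms will be estimated at each time point"), showing baseline proportions by arm beside it. The mixed models stay exploratory.

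The cost is a few sentences and 7 × 4 = 28 small models, plus 4 for the XQ. No new data, visits or subjects are needed. If r is 0, intervals are about 1.6% wider at 18 per arm and 1.1% wider at 25.
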